4.4. Patient Identification and Registration

The Investigator and the Investigator's study staff will identify potential patients for the study. Patients who are candidates for enrollment into the study will be evaluated for eligibility by the

Investigator to ensure that the inclusion and exclusion criteria have been satisfied and that the patient is eligible for participation in this clinical study.

All patients screened for the study will be assigned a unique screening number representing a combination of the site number and a sequential 3-digit number, which will be used to identify patients throughout their participation in the study. Screening numbers will be assigned sequentially starting at 001 (i.e.; the first patient screened at site 10 would be assigned screening number 10001). Once a patient number has been assigned, it cannot be reused.

4.5. Withdrawal of Patients

Patients will be informed that they have the right to withdraw from the study at any time for any reason, without prejudice to their medical care. The Investigator also has the right to withdraw patients from the study, after discussion with the sponsor, for any of the following reasons:

- AEs, which justify ceasing treatment. Specific predefined events for discontinuation, as well as additional guidelines for safety monitoring, are included in Appendices 11.4 – 11.7.
- Non-adherence to study drug regimen or protocol requirements.
- Non-compliance with instructions or failure to return for follow-up.
- Failure to demonstrate 5 kg of weight loss (or 5% if baseline body weight is <100 kg) at the end of the 10-week open label treatment phase.

If a patient is withdrawn from treatment or discontinued from the study, the primary reason is to be recorded in the source documents/case report form (CRF).

All patients who are no longer receiving active treatment prior to completing the ~ 1 year treatment period should be strongly encouraged to complete all remaining visits and procedures as outlined in the Schedule of Assessments in Section 6.

In case of withdrawal from the study (i.e. withdrawing consent), all adverse events should be followed as described in Section 7.4; any skin adverse experiences should continue to be followed, if at all feasible, for ~60-90 days to confirm near, or complete resolution (as has been shown in previous studies).

Rhythm will provide support for patient and caregiver travel, will make available visiting home health care professionals, and any other necessary logistical support to ease the burden on the patient to facilitate compliance.

5. STUDY TREATMENTS

5.1. Study Drugs

All study drugs are for investigational use only and are to be used only within the context of this protocol. All investigational study drugs (setmelanotide and placebo) will be supplied by Rhythm.

Setmelanotide drug product (RM-493-mPEG/DSPE formulation) is a sterile solution for injection. The product is manufactured at a concentration of 10.0 mg/mL.

Placebo will be vehicle.

Setmelanotide and placebo are clear, colorless to slightly opalescent solutions essentially free of visible particulates, and are suitable for a double-blind study. Setmelanotide and placebo will be administered as SC injection once daily.

All study drug must be kept in a secure, limited-access storage area at a temperature between 2°C to 8°C. Both setmelanotide and placebo are stable at room temperature for a short period that will allow patients to transport study drug home; ice packs and cooler bags will be provided for patients and caretakers who will travel long distances from the clinic. Patients will be encouraged to proceed directly home after clinic visits in which study drug is dispensed to minimize the amount of time the study drug is exposed to elevated temperatures.

A separate pharmacy manual with specific instructions will be provided to the investigative site.

There will be extensive training of patients in drug administration including educational materials. Study specific training materials will be provided to both the investigative staff and study participants and caregivers. Rhythm will provide extra placebo supplies for use during training.

5.2. Study Drug Dose and Administration

Study patients will receive study drug by SC injection once daily (administered in the morning). The dose titration phase will consist of a dose titration phase of up to 10 weeks. Once the patient's therapeutic dose is determined, the same dose/volume will be administered throughout the remainder of the study.

The goal is for the patient or their caretaker to successfully self-administer the study drug themselves at home. Given the rarity of LEPR patients, arrangements may be made for those who are not able to successfully self-administer the study drug to have assistance by a visiting home health care practitioner.

Patients and/or their caretakers (including home health practitioners) will be responsible for all procedures associated with study drug administration, i.e., drawing up, and self-administering the study drug once daily (including during the practice periods).

To ensure patients or their caregivers can successfully self-administer study drug, a training period in the clinic with placebo (or saline) during screening will occur before entering the open label dose titration phase. This training/practice period can occur as many times as necessary throughout the study to assure proper technique. The training/practice period does not pertain to the home health practitioners.

Patients will be required to fast overnight for all clinic visits. Water will be allowed throughout the fasting period.

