5.2.1. Dose Titration and Adjustments

Experience in the first two POMC patients and the 3 LEPR deficient patients enrolled in the investigator-initiated trial (RM-493-011), as noted above, has shown marked reductions in hunger and weight without revealing any new or unanticipated AEs to date. The efficacious dose in these patients has ranged from total daily doses of 1-2 mg of setmelanotide. However, due to the small number of POMC/LEPR deficient patients exposed to setmelanotide to date, careful increases in dose titrations will be conducted.

The first dose of setmelanotide will be administered at the start of the Dose Titration Phase beginning with week 1. Patients will return to the clinic every 2 weeks to assess for efficacy and if individual patient doses are to be titrated upwards (per Table 1 and Appendix 11.8). During the Dose Titration Phase, the patient's therapeutic dose will be identified. Doses should not be increased by more than 0.5 mg. Doses should not be adjusted after the dose titration phase has been completed unless discussed and approved by the Sponsor.

Table 1: Dose Titration Schedule

Dose Titration Week	Adult Dose (mg)	Adolescent Dose (mg)	Pediatric Dose (mg)
1-2	1.0	0.5	0.25
3-4	1.5	1.0	0.5
5-6	2.0	1.5	1.0
7-8	2.5	2.0	1.5
9-10	3.0*	2.5	2.0
11-12	NA	3.0*	2.5

*Can only escalate to 3.0 mg if approved by the participating country's competent authority, otherwise the maximum allowable dose is 2.5 mg.

For patients who may have reached the maximum dose but have not lost the target weight as described in Appendix 11.8, patients will be allowed to continue into the 10-week open label active treatment phase to allow the patient the opportunity to respond.

Although LEPR deficient patients have not been treated long term with setmelanotide, there is limited long term data in the two POMC deficient patients. This data demonstrates that even when BMI's near normalization, dose reductions have prompted increases in hunger scores until the resumption of the individual patients initially determined therapeutic dose. However, as experience is limited, during the 32-week Open Label Treatment Phase, if patients' body weight normalizes to an appropriate level (i.e. BMI <27 for adults or an age and gender value equivalent to <95th percentile for pediatrics or adolescents), a dose reduction may be considered upon consultation with the sponsor.

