[REDACTED] Menarche and menstrual history will be obtained in all females. Adrenarche staging will be performed. Testicular volumes will be documented by the Prader methodology for males, and breast development will be documented for females. Height will be measured during the Screening Period only for those patients \geq 18 years of age. Height will be measured per the [SOA](#) for those patients $<$ 18 years of age. Height (cm) will be measured, without shoes, socks or hats according to the SOA using a wall-mounted stadiometer. All measurements will be done in triplicate at each timepoint and recorded to the nearest 10th of a decimal place. The stadiometer should be calibrated at the time of use or within the previous four hours.

2 A comprehensive skin evaluation will be performed by a dermatologist. Any concerning lesions identified during the screening period will be biopsied and results known to be benign prior to first dose of setmelanotide. If the pre-treatment biopsy results are of concern, the patient will be excluded from the study.

3 Optional sub-studies for Investigative Sites that can perform these assessments and have patients willing and able to participate. In the event a site can perform multiple sub-studies, care needs to be taken in order to not overburden with multiple additional assessments/visits.

4 Urine pregnancy test may be performed to expedite availability of results prior to dosing on Dose Titration Day 1. All other pregnancy tests will be serum; dosing may continue with results pending.

5 Prior to study drug administration.

6 The Dose Titration phase will be a variable schedule lasting a minimum of 2 weeks and a maximum of 10 weeks, in which patients will return to the clinic approximately every 2 weeks to establish the individual patient's therapeutic dose per Appendix 11.8. Given the variable number of dose titration steps in the Dose Titration Phase, each Dose Titration Visit Number (V) will remain V2 with an alphabetized suffix added to each titration visit (i.e.; first dose titration at start of Week 1 = V2a, second dose titration at start of Week 3 = V2b, etc.). This will allow for the Visits to be appropriately tracked. Additionally, each dose titration visit will have the same pre- and post-dose assessments as outlined in the [SOA](#) (except for Anti-RM-493 antibodies and [REDACTED])

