28 Following collection of pre-meal (time 0) blood samples, patients will be given a standard oral glucose tolerance test. The following blood samples will be obtained during each OGTT: Blood glucose and insulin at approximately 30, 60 90 and 120 minutes after meal start. OGTT will not be performed for subjects with a diagnosis of Type 1 or Type 2 diabetes.

29 ~8 hours post-dose on Day 1 only.

30 ~8 hours post-dose.

31 To be collected at Study Day 15 and Day 29 during the dose titration phase (i.e. V2b and V2c or V2b and V3 if the patient's therapeutic dose is established at the first dose level)

32 A blood sample will be obtained at Screening for genotyping for mechanisms considered to be possibly related to the safety or efficacy response to the study medication (e.g., other obesity related genes).

33 [REDACTED]

34 [REDACTED]

35 For pediatric patients, weight will be measured every 2-3 weeks between visits during the additional 32-week open label treatment phase, at the patient's home by a parent or caregiver.

36 For pediatric patients only, Nutritional Counseling and Monitoring will be performed by an appropriate dietician or nutritionist (or equivalent) to ensure that pediatric patients have adequate nutritional/dietary intake to maintain proper growth and development. Additional laboratory assessments indicative of nutritional status may be monitored, as appropriate (e.g. albumin, vitamin D, total lymphocytes and IGF1).

37 Collect between 8 and 10 am

38 [REDACTED]

Once a patient's therapeutic dose has been established according to Appendix 11.8, no further dose titrations will occur, and patients will transition directly into the 10 week Open Label Active Treatment phase. Therefore, the Dose Titration phase will be a minimum of 2 weeks and a maximum of 10 weeks.

* For patients that reside a considerable distance from the clinic, these visits are optional clinic visits, and may be performed by the patient's local physician or home health care professionals.

+ If the visit is performed by a home health care professional, assessment may be performed at the next schedule in clinic visit.

^ For patients enrolled in France, the [REDACTED] are compulsory, and not optional.

† Test not conducted at this visit for patients 6 to 11 years.

** All screening bloodwork should be collected between Study Day -28 and -14 in order to ensure the WHO maximum cumulative blood volumes are not exceeded over the course of the study.

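### Section 5.2 and two schedule notes cap titration at 10 weeks, but Table 1 needs 12 for children and for adolescents going to 3.0 mg; Sections 3.1 and 3.2 also misstate the first pediatric step

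*Protocol*

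**What the plan says.** **Length.** Section 5.2 reads "The dose titration phase will consist of a dose titration phase of up to 10 weeks", and adds that once the therapeutic dose is known "the same dose/volume will be administered throughout the remainder of the study". Footnote 6 to Table 6-1 describes the phase as "lasting a minimum of 2 weeks and a maximum of 10 weeks". The unnumbered note closing the footnotes repeats that "the Dose Titration phase will be a minimum of 2 weeks and a maximum of 10 weeks".

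Other parts of the protocol give a longer phase:

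- The synopsis (trial design and study activities) and Section 3.1 give a range of 2 to 12 weeks.
- Section 5.5 lists 12 weeks as the longest titration and about 66 weeks as the longest participation.
- Table 1 in Section 5.2.1 has a row for weeks 11-12, with 2.5 mg for children and 3.0 mg for adolescents where the country has approved it.
- The blood-volume tables in Appendix 11.12 list six titration visits, 2a to 2f.

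**Step.** Section 3.1 gives starting doses of 1.0, 0.5 and 0.25 mg (adult, adolescent, child) and then increments of 0.5 mg every two weeks. Section 3.2 applies the 0.5 mg step explicitly to adolescents and children and sets a 2.5 mg pediatric maximum. Table 1 instead takes children from 0.25 to 0.5 mg first. Section 5.2.1 adds only a ceiling: "Doses should not be increased by more than 0.5 mg".

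**After titration.** Section 5.2.1 states: "Doses should not be adjusted after the dose titration phase has been completed unless discussed and approved by the Sponsor".

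**The concern.** The 10-week limit appears in the dosing section and in the schedule notes, which are the parts that sites work from. It removes the sixth dose level that Table 1 provides. Two sites could treat the same child differently and each point to protocol text. A dose held one level short could later be raised only with Sponsor approval.

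The patients exposed are those with the least margin. Under Section 3.2, titration stops once the weight or hunger target is met, so a patient who reaches level six has missed the target at every lower dose. That patient next meets the weight-loss requirement of 5 kg, or 5% if under 100 kg at baseline. Failing it ends treatment (Sections 3.1 and 4.5).

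The step wording raises a related problem at the other end of the ladder, the first dose increase in children aged 6 to 11.

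**Working it through.** **Weeks needed.** The inputs are the two-week dose levels in Table 1 and the country maximum of 2.5 or 3.0 mg in Section 3.1. Weeks = 2 × number of levels up to the maximum.

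| Group | Maximum | Levels | Weeks | Dose at week 10 |
|---|---|---|---|---|
| Adult | 2.5 mg | 4 | 8 | 2.5 mg |
| Adult | 3.0 mg | 5 | 10 | 3.0 mg |
| Adolescent | 2.5 mg | 5 | 10 | 2.5 mg |
| Adolescent | 3.0 mg | 6 | 12 | 2.5 mg |
| Child | 2.5 mg (all countries) | 6 | 12 | 2.0 mg |

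The 10-week figure fits adults, and adolescents limited to 2.5 mg. It fails for children everywhere, and for adolescents in the US, the UK and the Netherlands.

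**Shortfall if titration stops at week 10.**
- Child: (2.5 − 2.0)/2.5 = 20%.
- Adolescent where 3.0 mg is approved: (3.0 − 2.5)/3.0 = 17%.

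**Total duration in Section 5.5.** The phases are screening, titration, open label, withdrawal and open label.
- Minimum: 2 + 2 + 10 + 8 + 32 = 54 weeks, as stated.
- Maximum with 12 weeks of titration: 4 + 12 + 10 + 8 + 32 = 66 weeks, as stated.
- Maximum with 10 weeks of titration: 4 + 10 + 10 + 8 + 32 = 64 weeks, which is not the stated figure.

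**Visits.** 10/2 = 5 titration visits (2a to 2e), and 12/2 = 6 (2a to 2f). Appendix 11.12 has six.

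**Could 10 weeks mean the time to the last escalation?** No. Section 3.1 counts the final two weeks at the therapeutic dose as titration. The 2-week minimum in the same sentences uses that counting too.

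**Pediatric ladder.**
- Flat 0.5 mg steps from 0.25 mg: 0.25, 0.75, 1.25, 1.75, 2.25. The next value, 2.75, exceeds the 2.5 mg maximum.
- Table 1: 0.25, 0.5, 1.0, 1.5, 2.0, 2.5.

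No level after the first agrees, and the flat ladder never gives 2.5 mg. At week 3 the ratio is 0.75/0.5 = 1.5, so the flat step is 50% higher. The ceiling in Section 5.2.1 does not decide between them, because a first step of 0.25 mg and one of 0.5 mg both satisfy it.

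**The case against.** The strongest reply is that the protocol already resolves the conflict. Table 1 sits just below the Section 5.2 sentence, gives milligram doses by week and age group, and is where Section 5.2.1 sends the site. Footnote 24 sets no week limit: a patient whose therapeutic dose is not established returns for the next titration visit. Week 10 is nowhere written as a stopping rule, and stopping an unestablished child at 2.0 mg would itself breach footnote 24. This shows which text should govern, and it is why the fix follows Table 1. It does not remove a stated maximum from operative text.

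On the step, the reply is that Section 3.2 is a rationale section, Section 3.1 defers to Appendix 11.8, and no sentence prints 0.75 mg. That is fair. The 0.75 mg figure follows by arithmetic from the stated start and step, and is not a dose the protocol lists.

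Two further points stand in part:

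- Appendix 11.8 and the pharmacy manual were not seen, so how far sites would really diverge is uncertain.
- A level-six patient starts the therapeutic dose after 10 weeks and reaches the final treatment visit 52 weeks later. That is 62 weeks, or 62 × 12/52 = 14.3 months, just past the 10-14 month endpoint window in Section 8.1. This follows from Table 1 as it already stands and is not created by the correction. Section 8.2 includes data outside visit windows, which probably covers it.

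**Conclusion.** The concern holds on both points. The 10-week maximum is wrong for children in every country and for adolescents where 3.0 mg is approved. The flat 0.5 mg step is wrong for the first pediatric increase. Table 1, the six titration visits and the 66-week total identify the intended rule.

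The effect is on dosing: up to 20% below the intended top dose for a child and 17% for an adolescent, or a week-3 pediatric dose 50% above Table 1. Adults, and adolescents limited to 2.5 mg, are unaffected by the length error. Only patients who need level six are touched by it, probably few of the roughly 10. Section 5.2.1 reports of the five earlier patients that "The efficacious dose in these patients has ranged from total daily doses of 1-2 mg of setmelanotide", and the week-10 doses of 2.0 mg (child) and 2.5 mg (adolescent) already reach that range.

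The primary test and its power calculation do not depend on titration length and do not change. The correction should be made because the error lies in operative dosing text for children. The textual conflict is certain. How many sites would act on the wrong text is not known, and Appendix 11.8 was not available to check.

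**What to change.** - In Section 5.2, footnote 6 and the closing schedule note, replace the 10-week maximum with: *12 weeks (10 weeks for adults), per Table 1*. This is correct as an upper bound under either country maximum.
- In Sections 3.1 and 3.2, state: *the first pediatric step is from 0.25 mg to 0.5 mg, with 0.5 mg steps thereafter, per Table 1*.
- Confirm that Appendix 11.8 agrees.
- Leave the primary endpoint window as it is.

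The cost is a wording correction in five places. It adds no visits, procedures or patients, and changes neither the endpoint nor the analysis.

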5.2.1. Dose Titration and Adjustments

Experience in the first two POMC patients and the 3 LEPR deficient patients enrolled in the investigator-initiated trial (RM-493-011), as noted above, has shown marked reductions in hunger and weight without revealing any new or unanticipated AEs to date. The efficacious dose in these patients has ranged from total daily doses of 1-2 mg of setmelanotide. However, due to the small number of POMC/LEPR deficient patients exposed to setmelanotide to date, careful increases in dose titrations will be conducted.

The first dose of setmelanotide will be administered at the start of the Dose Titration Phase beginning with week 1. Patients will return to the clinic every 2 weeks to assess for efficacy and if individual patient doses are to be titrated upwards (per Table 1 and Appendix 11.8). During the Dose Titration Phase, the patient's therapeutic dose will be identified. Doses should not be increased by more than 0.5 mg. Doses should not be adjusted after the dose titration phase has been completed unless discussed and approved by the Sponsor.

Table 1: Dose Titration Schedule

Dose Titration Week	Adult Dose (mg)	Adolescent Dose (mg)	Pediatric Dose (mg)
1-2	1.0	0.5	0.25
3-4	1.5	1.0	0.5
5-6	2.0	1.5	1.0
7-8	2.5	2.0	1.5
9-10	3.0*	2.5	2.0
11-12	NA	3.0*	2.5

*Can only escalate to 3.0 mg if approved by the participating country's competent authority, otherwise the maximum allowable dose is 2.5 mg.

For patients who may have reached the maximum dose but have not lost the target weight as described in Appendix 11.8, patients will be allowed to continue into the 10-week open label active treatment phase to allow the patient the opportunity to respond.

Although LEPR deficient patients have not been treated long term with setmelanotide, there is limited long term data in the two POMC deficient patients. This data demonstrates that even when BMI's near normalization, dose reductions have prompted increases in hunger scores until the resumption of the individual patients initially determined therapeutic dose. However, as experience is limited, during the 32-week Open Label Treatment Phase, if patients' body weight normalizes to an appropriate level (i.e. BMI <27 for adults or an age and gender value equivalent to <95th percentile for pediatrics or adolescents), a dose reduction may be considered upon consultation with the sponsor.

5.3. Method of Assigning Patients to Treatment

Patients who qualify for the study will return to the site on Day 1 of the dose titration phase. Prior to initiating open label dose titration, the Investigator will ensure that the patient continues to meet inclusion and exclusion criteria, and perform all pre-dose procedures.

Once the pre-dose procedures are completed, the patient deemed eligible for the study, the first dose of setmelanotide will be administered in the presence of the Investigator or the Investigator's research staff.

Since this is an open label study, except for the double-blind withdrawal period, all patients will be assigned to active treatment except for during the double-blind withdrawal phase.

5.4. Blinding, Packaging, and Labeling

5.4.1. Blinding and Breaking the Blind

This study will be open label, except for the 8-week double-blind, placebo controlled variably timed withdrawal period. Blinding will be accomplished so that all patients and study-related staff remain blinded to study drug and patient assignment.

The Investigator, study site staff, clinical research organization staff providing site management and Medical Monitor will not have access to the actual treatment sequence being administered during the 8-week double-blind placebo controlled phase, except in the case of an emergency. Breaking the blind for a patient should be done only in the event of a medical emergency where the identity of study drug is necessary to appropriately treat the patient. The request to break the blind should be discussed with the Medical Monitor and Rhythm, whenever possible. If the blind is broken, the reason, when and how the blind was broken will be documented. Every attempt will be made to maintain the blind throughout the study.

